4.1 General Concomitant Medication and Supportive Care Guidelines

Subjects will not receive any live/attenuated vaccine (eg, varicella, zoster, yellow fever, rotavirus, oral polio and measles, mumps, rubella (MMRI) during treatment and until 100 days post-last dose.

Otherwise, there are no restrictions on concomitant medications or supportive care medications.

If clinically indicated, palliative radiation therapy to non-target lesions is permitted.

4.2 Criteria for Removal from Study

Subjects will be removed from study if they have disease progression; unacceptable adverse events in the opinion of the subject or the investigator; withdrawal of consent; non-compliance; or if subject is female and has become pregnant.

4.3 Alternatives

Alternatives include other systemic therapies, other clinical trials, or supportive care (NOTE: corticosteroid restriction is only an eligibility criteria and not an on-study concurrent medication restriction).

5. INVESTIGATIONAL AGENT

5.1 Ipilimumab (Yervoy)

Ipilimumab (BMS-734016, MDX010, MDX-CTLA4) is a fully-human monoclonal immunoglobulin (Ig) G1κG1κ specific for human cytotoxic T-lymphocyte antigen 4 (CTLA-4, CD-152), which is expressed on a subset of activated T cells. CTLA-4 is a negative regulator of T-cell activity. Ipilimumab is a monoclonal antibody (mAb) that binds to CTLA-4 and blocks the interaction of CTLA-4 with its ligands, CD80/CD86. Blockade of CTLA-4 has been shown to augment T-cell activation and proliferation, including the activation and proliferation of tumor-infiltrating T-effector cells. Inhibition of CTLA-4 signaling can also reduce T-regulatory cell (Treg) function, which may contribute to a general increase in T-cell responsiveness, including the anti-tumor response.

5.1.1 Effects in Humans

Bristol-Myers Squibb (BMS) and Medarex, Inc (MDX, acquired by BMS in Sep 2009) have co-sponsored an extensive clinical development program for ipilimumab, encompassing more than 22,571 subjects (total number of subjects enrolled in ipilimumab studies) in several cancer types in completed and ongoing studies, including a compassionate use program.

Ipilimumab 3 mg/kg has been approved for use in advanced melanoma in over 47 countries, including the United States (US, 25 Mar 2011), the European Union

(EU, 13 Jul 2011), and Australia (Jul 2011). Ipilimumab 10 mg/kg is approved as adjuvant treatment of unresectable or metastatic melanoma in the US. Ipilimumab is approved in the EU for the treatment of adolescents and in the US for the treatment of melanoma in pediatric subjects.

Additionally, ipilimumab has been approved for the following indications:

- Treatment of subjects with intermediate or poor risk, previously untreated advanced renal cell carcinoma, in combination with nivolumab.
- Treatment of adult and pediatric subjects 12 years of age and older with microsatellite instability-high (MSI-H) or mismatch repair deficient (dMMR) metastatic colorectal cancer that has progressed following treatment with a fluoropyrimidine, oxaliplatin, and irinotecan, in combination with nivolumab. This indication is approved under accelerated approval based on overall response rate and duration of response. Continued approval for this indication may be contingent upon verification and description of clinical benefit in confirmatory trials.

5.1.2 Availability

Bristol-Myer Squibb will be providing this agent.

5.1.3 Agent Ordering

This agent will be requested from Bristol-Myers Squibb in advance. A supply of the drug will be available at Stanford investigational pharmacy at all times.

5.1.4 Agent Storage and Accountability

Per the Investigator Brochure, vials of ipilimumab injection must be stored at 2°C to 8°C (36°F to 46°F) and protected from light and freezing. Ipilimumab injection may be stored undiluted (5 mg/mL) or following dilution in 0.9% sodium chloride injection or 5% dextrose injection in PVC, non-PVC/non-DEHP, or glass containers for up to 24 hours at 2°C to 8°C or room temperature/room light.

This agent will be kept secure per Stanford investigational pharmacy SOP.

5.2 Nivolumab (Opdivo)

Nivolumab (also referred to as BMS-936558, MDX1106, or ONO-4538) is a human monoclonal antibody (HuMAb; immunoglobulin G4 [IgG4]-S228P) that targets the programmed death-1 (PD-1) cluster of differentiation 279 (CD279) cell surface membrane receptor. PD-1 is a negative regulatory molecule expressed by activated T and B lymphocytes.¹ Binding of PD-1 to its ligands, programmed death-ligands 1 (PD-L1) and 2 (PD-L2), results in the down-regulation of lymphocyte activation.

Inhibition of the interaction between PD-1 and its ligands promotes immune responses and antigen-specific T-cell responses to both foreign antigens as well as self-antigens. Nivolumab is expressed in Chinese hamster ovary (CHO) cells and is produced using standard mammalian cell cultivation and chromatographic purification technologies.

The clinical study product is a sterile solution for parenteral administration.

5.2.1 Effects in Humans

The pharmacokinetics (PK), clinical activity, and safety of nivolumab have been assessed in subjects with non-small cell lung cancer (NSCLC), melanoma, clear-cell renal cell carcinoma (RCC), classical Hodgkin Lymphoma (cHL), urothelial carcinoma (UC), squamous cell carcinoma of the head and neck (SCCHN), in addition to other tumor types.

Nivolumab monotherapy is approved in multiple regions, including the US and EU, for unresectable or metastatic melanoma, previously treated metastatic NSCLC, previously treated advanced RCC, previously treated relapsed or refractory cHL, previously treated advanced or metastatic UC, and for the treatment of previously treated recurrent or metastatic SCCHN; it is also approved for previously treated CRC, previously treated HCC, and the adjuvant treatment of melanoma in the US.

In addition, nivolumab has been approved for use in combination with ipilimumab for RCC in the US and unresectable melanoma in multiple countries, including the US and EU.

5.2.2 Availability

Bristol-Myers Squibb will be providing this agent.

5.2.3 Agent Ordering

This agent will be requested from Bristol-Myers Squibb in advance. A supply of the drug will be available at Stanford investigational pharmacy at all times.

5.2.4 Agent Storage and Accountability

Per the Investigator Brochure, vials of nivolumab injection must be stored at 2°C to 8°C (36°F to 46°F) and protected from light and freezing. The unopened vials can be stored at room temperature (up to 25°C, 77°F) and room light for up to 48 hours.

This agent will be kept secure per Stanford investigational pharmacy SOP.

5.3 Cryoablation

Cryoablation of the tumors occur between investigational agent treatment Cycles 1 and 2, and will be performed according to standard procedures. The cryotherapy devices will be FDA-approved cryoablation systems that in current use within the Stanford University Medical Center.

Prior to the cryoablation procedure, the interventional radiologist will review cross-sectional imaging studies to formulate a treatment plan, including identifying the target lesions appropriate for treatment; the number and type of cryoablation probes needed; and optimal percutaneous access approach. As the goal of the cryotherapy is to enhance systemic immunotherapy, the cryoablation will most commonly be subtotal. For lesions that are in close proximity to freeze-sensitive tissues, such as bowel or skin, the cryoablation treatment will be performed with a safe distance (≥ 1 cm) between the edge of the tissue to be frozen (the “iceball”) and the freeze-sensitive tissue.

The cryoablation procedure will be performed with moderate sedation or general anesthesia in a CT procedure room. A limited CT will be obtained and the desired

access sites will be marked on the subject's skin. After sterile preparation of the treatment field and application of local anesthesia, cryoablation probes will be sequentially placed percutaneously into the target lesion(s) using CT and/or ultrasound guidance. After all cryoablation probes are positioned appropriately, cryoablation will be performed with 1 or more freeze-thaw cycles. Iceball growth will be monitored by CT. The probes will then be removed and sterile dressings applied.

In brief, a total of 20 minutes of freezing time will be administered to the tumor in 2 or 3 freeze-thaw cycles. Care will be taken to avoid off-target ablation of sensitive structures such as bowel and skin. The procedures will be performed under either moderate sedation, monitored anesthesia care (conscious sedation), or general anesthesia, depending on the subject's ability to tolerate positioning for the anticipated duration of the procedure. The risks of ablation include hemorrhage, infection, pneumothorax, and injury to off-target structures. With any procedure there is a small risk of death. After ablation, the subject can expect discharge to home within 23 hours in most circumstances.

6. DOSE MODIFICATIONS

There will be no dose modifications for the investigational agents.

Per-subject stopping rule

Subjects will be monitored for toxicity at every study visit during the treatment phase (through 10 weeks). As defined by the current US package inserts (USPIs) for nivolumab and ipilimumab, treatment will be withheld for the related adverse events (toxicities) specified therein, and additionally by the discretion of the investigator. Treatment may be resumed in accordance with the USPIs. In the event that toxicity is judged to be excessive, treatment will be terminated with one or both agents. Particular attention will be given to events that might be an overlapping toxicity.

7. ADVERSE EVENTS AND REPORTING PROCEDURES

7.1 Potential Adverse Events

7.1.1 Ipilimumab (see appendix D for treatment algorithm)

Inflammatory Events (Immune-related Adverse Events or Immune-mediated Adverse Reactions)

Blockade of CTLA-4 by ipilimumab leads to T-cell activation, with the potential for clinical inflammatory AEs primarily involving the skin (dermatitis/pruritus), GI tract (diarrhea/colitis), liver (hepatitis), endocrine glands (eg, hypophysitis and adrenal or thyroid abnormalities), and other less frequent organs (eg, uveitis/episcleritis). The majority of these inflammatory AEs initially manifest during treatment; however, a minority occur weeks to months after discontinuation of ipilimumab. The majority of the inflammatory AEs are reversible with the guidance issued below.

- Gastrointestinal Toxicities

The most common site for ipilimumab-induced GI toxicity was the lower GI tract, and the most common presentation was mild to severe diarrhea or colitis with occasional bloody stools. In some cases, diarrhea began as mild and then worsened. Constipation was

rarely associated with ipilimumab administration. Delay in corticosteroid treatment may be associated with a poor outcome for subjects with high-grade diarrhea.

- Liver Toxicities

Subjects receiving ipilimumab may develop elevations in LFTs in the absence of clinical symptoms. Occasionally, subjects may present with symptoms, including right upper quadrant abdominal pain or unexplained vomiting. Most cases of inflammatory hepatitis responded to high-dose corticosteroids (IV route recommended).

- Endocrine Toxicities

The most common inflammatory endocrine toxicities are hypophysitis and hypopituitarism, secondary cortisol deficiency (hypoadrenalinism), hypothyroidism or thyroiditis. Symptoms of hypopituitarism and other endocrine toxicities were generally controlled with appropriate hormone replacement.

- Skin Toxicities

The most common inflammatory skin toxicities are rash and pruritus, mostly mild to moderate in severity. Two cases of fatal treatment-related toxic epidermal necrolysis have been reported in clinical trials.

- Neurological Toxicities

Neurological manifestations may include motor and/or sensory neuropathy. Fatal Guillain-Barre syndrome and cases of myasthenia gravis have been reported in clinical trials. Unexplained motor neuropathy, muscle weakness, or sensory neuropathy should be evaluated, and non-inflammatory causes such as infections, metabolic disorders, and medications should be excluded.

- Other Toxicities

Ocular inflammation can be manifested as episcleritis or uveitis. Other presumed inflammatory events reported include, arthritis/arthralgia, pneumonitis, pancreatitis, autoimmune (aseptic) meningitis, autoimmune nephritis, pure red cell aplasia, noninfective myocarditis, polymyositis, eosinophilia, pericarditis, urticaria (2%), large intestinal ulcer, esophagitis, acute respiratory distress syndrome, renal failure, infusion reactions, and myasthenia gravis.

7.1.2 Nivolumab (see appendix D for treatment algorithm)

- Pulmonary toxicities

Subjects can present with either asymptomatic radiographic changes (eg, focal ground glass opacities and patchy infiltrates) or with symptoms of dyspnea, cough, or fever. All subjects with Grade 3 to 4 pneumonitis should discontinue nivolumab and initiate treatment with high doses of corticosteroids.

- Gastrointestinal toxicities

Most cases present with diarrhea. However diverticular perforation should also be considered when subjects present with abdominal pain and fevers.

- Hepatic toxicities

Early recognition and treatment of elevated LFTs and drug-induces liver injury are critical to their management. The principal treatment for high-grade hepatic AEs is corticosteroids.

- Endocrinopathies

The events are typically identified through either routine periodic monitoring of specific laboratories (eg, TSH) or as part of a work-up for associated symptoms (eg, fatigue). Moderate- to high-grade cases were managed with hormone replacement therapy and, in some cases, with the addition of corticosteroids.

- Skin toxicities

The most common skin toxicities include rash and pruritus. Rashes are typically focal with a maculopapular appearance occurring on the trunk, back, or extremities. Topical corticosteroids can be used for some cases of rash. Anti-histamines can be used for some cases of pruritus.

- Renal toxicities

Elevated creatinine and biopsy-confirmed tubulointerstitial nephritis and allergic nephritis are seen infrequently.

- Neurologic toxicities

Neurologic AEs can manifest as central abnormalities (eg, aseptic meningitis, encephalopathy, or encephalitis) or peripheral sensory/motor neuropathies (eg, Guillain-Barre Syndrome, myasthenia gravis complicated with sepsis and fatality). The onset has been observed as early as after a single treatment with the nivolumab + ipilimumab combination.

- Infusion Reactions

Infusion reactions, including high-grade hypersensitivity reactions, following administration of nivolumab are uncommon. Investigators are advised to monitor for fever, chills, shakes, itching, rash, hypertension or hypotension, or difficulty in breathing during and immediately after administration of nivolumab. Study protocols provide explicit guidance on the management of infusion-related reactions.

- Lipase/Amylase Elevations

In studies evaluating the safety of the nivolumab + ipilimumab combination in multiple tumor types, lipase and amylase levels were systematically monitored, and elevations in any grade of lipase/amylase were consistently noted in approximately 10% to 30% of subjects. Very few subjects reported associated symptoms.

- Uveitis and Visual Complaints

Uveitis may occur more frequently with nivolumab + ipilimumab combination therapy than with nivolumab monotherapy or nivolumab in combination with other therapies. An ophthalmologist should evaluate visual complaints with examination of the conjunctiva, anterior and posterior chambers, and retina. Topical corticosteroids may be used to

manage low-grade events. Low-grade events that do not resolve and high-grade events should be managed with systemic corticosteroids. Rare cases of granulomatous panuveitis with exudative retinal detachment have been observed and are often associated with neurologic and cutaneous manifestations.

- Other Immune-mediated Adverse Events

Rare cases of myotoxicity (myositis, myocarditis, and rhabdomyolysis), some with fatal outcome, have been reported with nivolumab or nivolumab in combination with ipilimumab.

For Grade 3 myocarditis, nivolumab or nivolumab in combination with ipilimumab should be permanently discontinued.

7.2 Adverse Event Reporting

Adverse events will be graded according to CTCAE v5. Adverse events will be recorded from the time the subject signs informed consent and for 30 days after the last dose of study drug. Adverse Events will be clearly noted in source documentation and listed on study specific Case Report Forms (CRFs). The Protocol Director (PD) or designee will promptly assess each Adverse Event (AE) to determine whether it is unexpected according to the Investigator's Brochure; this protocol, and/or the informed consent document, and related to the both the study drug and the investigation itself. All Serious Adverse Events (SAEs) will be tracked until resolution, or until 100 days after the last dose of the study drug.

Reporting Serious Adverse Events (SAEs)

Any adverse event meeting the definition of a 21CFR§312.32 serious adverse event (SAE) that occurs during the clinical study and for 100 days after the last dose of study drug must be recorded as an on-study SAE. Attribution of the SAE to study drug should follow the standard attribution and grading system as specified by CTEP (<http://ctep.cancer.gov/reporting/adeers.html>, see table below).

Attribution of Adverse Events

Code	Descriptor	Definition
1	Unrelated	The adverse event is clearly not related to the investigational agent(s)
2	Unlikely	The adverse event is doubtfully related to the investigational agent(s)
3	Possible	The adverse event may be related to the investigational agent(s)
4	Probable	The adverse event is likely related to the investigational agent(s)
5	Definite	The adverse event is clearly related to the investigational agent(s)

FDA

Events that meet the 21CFR§312.32 definition of a serious, unexpected, suspected adverse reaction (SUSAR, ie, serious, unexpected, and related SAE) will be reported to the investigator's IND as a serialized submission on the Form FDA 3500A (MedWatch

form for Mandatory Reporting), in accordance with the timelines defined at 21CFR§312.32.

Drug Manufacturer (Bristol Myers Squib)

SAEs, whether related or not related to study drug, and any on-study pregnancies, will be reported within 24 hours to Bristol-Myers Squibb (**SAE Email Address: [contact]**; **SAE [contact]). The SAE will be reported on the [Form FDA 3500A](#) (MedWatch form for Mandatory Reporting) if used per the above; or the [Form FDA 3500](#) (MedWatch form for Voluntary Reporting) or the Council for International Organizations of Medical Sciences ([CIOMS](#) form).

Stanford Cancer Institute (SCI) Data Safety Monitoring Committee (DSMC)

SAEs, CTCAE Grade 3 and above, whether related or not related to study drug; all on-study pregnancies; and all subsequent follow-ups must be reported to the Stanford Cancer Institute Data and Safety Monitoring Committee (DSMC) via [contact] within 24 hours (1 business day) of becoming aware of the event. The SAE will be reported using the CCTO SAE CRF plus the Form FDA 3500A (MedWatch form) if prepared per above.

Institutional Review Board (IRB)

Events that meet the 21CFR§312.32 definition of a serious, unexpected, suspected adverse reaction (SUSAR) which occurred as a result of the study intervention(s) or protocol-specific procedures, including diagnostic procedures, will be reported to the local IRB of record. If a Form FDA 3500A (MedWatch form) was prepared per the above, this should be part of the report.

Following review by the SCI DSMC, the committee may issue an assessment that an event met the criteria of an IRB definition of “Unanticipated Problem (UP).” Upon notification of such determination, the investigator will, if not previously reported to the IRB as a UP, submit a UP report of the event within 10 working days of DSMC notification, or within 5 working days for deaths or life-threatening events.

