9. STUDY CALENDAR

	Pre-Study/ Baseline	Wk 1	Wk 4 (± 3 d)	Wk 7 (± 3 d)	Wk 10 (± 3 d)	Maintenance Every 4W± 1W	Off-study (post-30 dy ± 1 wk)	Follow-up ⁱ
Investigational Agents		X	X	X	X	X		
Cryoablation			X					
Informed Consent	X							
Demographics	X							
Medical History	X							
Concomitant medications	X	X	X	X	X	X	X	
Physical exam	X	X	X	X	X	X	X	
Vital signs	X	X	X	X	X	X	X	
Height	X							
Weight	X	X	X	X	X	X	X	
Performance status	X	X	X	X	X	X	X	
PRO-CTCAE Questionnaire ^a		X	X	X	X	X	X	
CBC with differential and platelets ^b	X	X	X	X	X	X	X	
Serum chemistry ^b	X	X	X	X	X	X	X	
EKG	X					(as clinically indicated)		
Adverse event evaluation ^c	X	X	X	X	X	X	X	
Tumor measurements ^d	X				X	X		
Radiologic evaluation (CT, MRI, X-ray) ^d	X				X	X ^d		
β-HCG ^e	X	X	X ^e	X	X	X ^e		
Other tests, as appropriate ^f	X		X					
Other correlative studies ^g		X	X	X	X		X	

- a. PRO-CTCAE Questionnaire will be completed by patients at each study visit before any assessments are performed. Questionnaires in English, Spanish, and traditional Chinese are attached in Appendix F.
- b. Metabolic comprehensive includes: albumin, alkaline phosphatase, ALT (SGPT), AST (SGOT), urea nitrogen, calcium, chloride, CO₂, creatinine, glucose, globulin, potassium, sodium, total bilirubin, total protein. These labs should be done at baseline within 14 days of first treatment, and within 72 hours of day 1 of each subsequent treatment.
- c. Adverse events are based on Common Terminology Criteria for Adverse Events (CTCAE) v5.0 Publish Date: 27 November 2017. Adverse events will be recorded from the time the subject signs informed consent through and including 30 days after the last dose of study drug. All serious adverse events will be tracked until resolution, or until 100 days after the last dose of study drug.

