- d. Tumor measurements are based on RECIST v1.1 and irRECIST criteria (Appendices C & D). Scans will be done at baseline within 28 days of 1st treatment and then after dose 4 of immunotherapy (W 10 dose). This scan should be done at week 14 ± 1 week and every 12 weeks ± 1 week, once subjects start maintenance nivolumab. Ablated tumors will not be included as part of the treatment response assessment, ie, disease response; measurable disease; or tumor progression, by either RECIST or irRECIST. The baseline measurements will be done before treatment, and follow-up measurements will be done after 4 doses of ipilimumab and nivolumab (12 weeks), then every 12 weeks thereafter. At Investigator's discretion, imaging of known sites of disease is recommended.
- e. Serum β-HCG: Women of child-bearing potential are required to have a negative pregnancy test within 24 hours (eligibility criteria) prior to the initial administration of study drug, then every 3 to 4 weeks (± 1 week) during the study (this test can be omitted if subject is post-menopausal by either surgery or elevated FSH).
- f. ACTH, serum cortisol, TSH, free T4, CRP, ESR.
- g. Archival tumor sample must be available at baseline. All subsequent biopsies will be collected in paraffin for research purposes and standard diagnostics. Blood will be collected at baseline, and prior to treatment dose on weeks 1, 4, 7, 10 and during the off-study visit. Off study visit with a ± 1 week.
- h. Per protocol cryoablation is required to be performed before Week 4 administration of ipilimumab and nivolumab. (between Cycle 1 and Cycle 2), at the discretion of the investigator.
- i. Safety follow-up: After the off-study visit, there will be two additional follow-up phone call/or retrieval of medical records that occur every 35 days ± 1 week to collect information on participants' health status.

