- a visit to the emergency room or other hospital department < 24 hours, that does not result in admission (unless considered an important medical or life-threatening event)
- elective surgery, planned prior to signing consent
- admissions as per protocol for a planned medical/surgical procedure
- routine health assessment requiring admission for baseline/trending of health status (eg, routine colonoscopy)
- Medical/surgical admission other than to remedy ill health and planned prior to entry into the study. Appropriate documentation is required in these cases.
- Admission encountered for another life circumstance that carries no bearing on health status and requires no medical/surgical intervention (eg, lack of housing, economic inadequacy, caregiver respite, family circumstances, administrative reason).
- Admission for administration of anticancer therapy in the absence of any other SAEs (applies to oncology protocols)

ADVERSE EVENT Collection and REPORTING INFORMATION:

- All Serious Adverse Events (SAEs) that occur following the subject's written consent to participate in the study through 100 days of discontinuation of dosing must be reported to BMS Worldwide Safety, whether related or not related to study drug. If applicable, SAEs must be collected that relate to any later protocol-specified procedure (eg, a follow-up skin biopsy).
- Following the subject's written consent to participate in the study, all SAEs, whether related or not related to study drug, are collected, including those thought to be associated with protocol-specified procedures. The investigator should report any SAE occurring after these aforementioned time periods, which is believed to be related to study drug or protocol-specified procedure.
- An SAE report should be completed for any event where doubt exists regarding its seriousness;
- If the investigator believes that an SAE is not related to study drug, but is potentially related to the conditions of the study (such as withdrawal of previous therapy or a complication of a study procedure), the relationship should be specified in the narrative section of the SAE Report Form.

An appropriate SAE form (Medwatch form) should be used to report SAEs to BMS. If you prefer to use your own Institutional form, it must be reviewed by the BMS Protocol Manager prior to study initiation to ensure that at a minimum all of the data elements on

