- Non-serious AE information should also be collected from following the subject's written consent to participate in the study.

Non-serious Adverse Event Collection and Reporting

The collection of non-serious AE information should begin following the subject's written consent to participate in the study. All non-serious adverse events (not only those

deemed to be treatment-related) should be collected continuously during the treatment period and for a minimum of 30 days following the last dose of study treatment.

Non-serious AEs should be followed to resolution or stabilization, or reported as SAEs if they become serious. Follow-up is also required for non-serious AEs that cause interruption or discontinuation of study drug and for those present at the end of study treatment as appropriate.

Laboratory Test Abnormalities

All laboratory test results captured as part of the study should be recorded following institutional procedures. Test results that constitute SAEs should be documented and reported to BMS as such.

The following laboratory abnormalities should be documented and reported appropriately:

- any laboratory test result that is clinically significant or meets the definition of an SAE
- any laboratory abnormality that required the participant to have study drug discontinued or interrupted
- any laboratory abnormality that required the subject to receive specific corrective therapy.

It is expected that wherever possible, the clinical rather than laboratory term would be used by the reporting investigator (eg, anemia versus low hemoglobin value).

Pregnancy

If, following initiation of the investigational product, it is subsequently discovered that a study participant is pregnant or may have been pregnant at the time of investigational product exposure, including during at least 5 half-lives after product administration, the investigational product will be permanently discontinued in an appropriate manner (eg, dose tapering if necessary for participant).

The investigator must immediately notify [contact] of this event and complete one of the following forms within 24 hours of awareness of the event via either the CIOMS, MedWatch or appropriate Pregnancy Surveillance Form in accordance with SAE reporting procedures.

Protocol-required procedures for study discontinuation and follow-up must be performed on the participant.

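### New non-serious related adverse events 31 to 100 days after the last dose need not be recorded, so Outcome 4 may be biased low

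*Combined protocol and SAP*

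**What the plan says.** **Recording window.** Section 7.2: "Adverse events will be recorded from the time the subject signs informed consent and for 30 days after the last dose of study drug". Footnote c of the Study Calendar (section 9) gives the same limit: "through and including 30 days after the last dose of study drug". The calendar's adverse event row is marked up to the off-study visit and has no mark under Follow-up.

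**Serious events.** Section 7.2 treats them separately: those occurring during the study and "for 100 days after the last dose of study drug must be recorded as an on-study SAE". Appendix E goes further: "The investigator should report any SAE occurring after these aforementioned time periods, which is believed to be related to study drug".

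**Non-serious events in Appendix E.** Collection is to continue "for a minimum of 30 days following the last dose of study treatment", so 30 days is a floor there.

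**Onset.** Section 7.1.1 says of ipilimumab: "The majority of these inflammatory AEs initially manifest during treatment", and then that "a minority occur weeks to months after discontinuation of ipilimumab".

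**Contacts after the off-study visit.** Footnote i, labelled as safety follow-up, plans "two additional follow-up phone call/or retrieval of medical records that occur every 35 days". Their stated purpose is to learn the participant's health status; adverse event entry is not mentioned.

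**The outcome affected.** Outcome 4 (section 10.1) is the total number of adverse events judged possibly, probably or definitely related. It has no restriction to serious events, and its timeframe is 24 months. It serves the secondary safety objective in section 1.2.

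**The concern.** The outcome is wider than the data collection behind it. Outcome 4 takes in every related event, but from day 31 after the last dose the plan requires only serious ones to be recorded. A rash, or an endocrine event managed with hormone replacement, that starts on day 50 and does not meet the serious definition would be absent from the count. So would a Grade 3 event that is severe but not serious.

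The protocol itself describes delayed onset and already contacts subjects during the unrecorded period. The omission can only lower the count. At stake is whether the description of tolerability covers the period in which the protocol expects some immune events to appear.

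**Working it through.** No power or error-rate figure is involved. The check is calendar arithmetic plus a comparison of clocks.

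**1. Do the planned contacts reach the 100-day limit for serious events?**
Inputs: off-study visit at day 30 ± 7 (calendar header); two contacts 35 days apart, each ± 1 week (footnote i).
- First contact: 30 + 35 = day 65.
- Second contact: 30 + 35 + 35 = day 100, which matches the window in section 7.2.
- If the tolerance is anchored to day 100, the last contact falls on days 93 to 107.
- If the tolerances accumulate, it falls between 23 + 28 + 28 = day 79 and 37 + 42 + 42 = day 121.

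**2. Length of the gap for non-serious events.**
100 − 30 = 70 days. This is calendar time; it is not a share of the risk.

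**3. Who falls into the gap?**
The onset statement in section 7.1.1 counts from stopping ipilimumab, which ends after four doses (weeks 1, 4, 7 and 10). The recording window counts from the last dose of any study drug.
- Last dose of both agents at week 10: adverse event recording ends at 10 + 30/7 = week 14.3, and recording of serious events at 10 + 100/7 = week 24.3.
- Last nivolumab dose D days after the last ipilimumab dose: recording reaches D + 30 days after ipilimumab. It covers 100 days after ipilimumab once D is at least 100 − 30 = 70 days, or 10 weeks.

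The gap that section 7.1.1 supports therefore lies with subjects who stop during induction or within about 10 weeks of its end. The documents do not say how many that will be. As an illustration only, section 12 cites about 60% progression-free at 3 months for approved drugs. If that applied here, 0.40 × 28 = 11.2, so about 11 of 28 subjects would have progressed or died by then, and section 4.2 removes subjects at progression.

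**4. How many subjects might be affected?**
The documents give no late-onset rate. Let p be an assumed proportion of 28 subjects with a first related non-serious event on days 31 to 100. The expected number is 28p, and the chance of at least one is 1 − (1 − p)^28.

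| Assumed p | Expected subjects | Chance of at least one |
|---|---|---|
| 2% | 0.6 | 43% |
| 5% | 1.4 | 76% |
| 10% | 2.8 | 95% |
| 20% | 5.6 | 99.8% |

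The range runs from less than one subject to nearly six and is set entirely by the assumption. Outcome 4 counts events, so these figures are not in its units.

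**5. Outcome 4 timeframe.**
Assume that the 24 months of maximum treatment and the 24 months of Outcome 4 both run from first treatment. A subject treated to the maximum is then under adverse event recording until about month 25. One hundred days (100/30.4 = 3.3 months) takes follow-up to about month 27.3. A 24-month timeframe cuts both off. For a subject who stops at week 10, the same timeframe implies about 104 weeks of coverage, although recording ends near week 14.

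**The case against.** A reader might infer that the plan misses late immune toxicity in general. It does not. Serious events are recorded to day 100, and related ones are reportable after that. Appendix E's definition of serious includes important medical events, and it asks for a report where seriousness is in doubt. Potential drug-induced liver injury follows the serious-event timeline, so hepatitis is a poor example of the gap. Non-serious events must be followed to resolution or stabilization, so an event that began before day 30 is not lost. All of this stands and confines the point to new-onset, non-serious events.

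A reader might also see a contradiction between section 7.2 and Appendix E. A 30-day window satisfies a 30-day minimum, so the texts are compatible. This is a design choice.

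The onset argument is also limited. Section 7.1.1 puts most inflammatory events on treatment and speaks of a minority afterwards, and the nivolumab section makes no comparable statement about onset after stopping. Maintenance visits include adverse event evaluation. This stands, and it is why the gap sits mainly with early stoppers.

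Finally, Outcome 4 is a descriptive count in a single-arm trial, and section 12 attaches no toxicity threshold to it. No formal decision changes. That limits the weight of the point, but the count would still fall short of its own definition. The change is cheap, and any error runs in a known direction.

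**Conclusion.** The point holds in a narrow form. New related non-serious events on days 31 to 100 after the last dose are not required to be recorded, although Outcome 4 would count them and contacts already exist in that period. Outcome 4 may therefore be biased low, chiefly for subjects who stop during or soon after induction.

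The size is unknown. The 70-day gap follows from the documents, but the number of events in it does not. That any were missed remains a plausible inference that the documents cannot confirm. The direction rests on two premises: the plan is followed as written, and at least some delayed events are non-serious. The primary response analysis and the two-stage rule are untouched. This is a low-cost improvement to a secondary safety outcome.

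**What to change.** - In section 7.2 and calendar footnote c, require all possibly, probably or definitely related adverse events, serious or not, to be recorded through 100 days after the last dose.
- Add an adverse event mark under Follow-up in the calendar, and state in footnote i that the two contacts collect related adverse events. Because the tolerance allows the last contact before day 100, say how the remaining days are covered, for example by a later record review.
- Align the Outcome 4 timeframe with this window (through 100 days after the last dose), so that events after month 24 in subjects treated to the maximum are not cut off. Appendix E's minimum remains satisfied.

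**Cost.** No new visit is needed. The change brings some extra adverse event entry and a slightly less favourable count. Attribution becomes harder once a subject starts another therapy. Capture of asymptomatic laboratory events will be incomplete: the contacts are by telephone or record retrieval, and no study laboratory tests are scheduled after the off-study visit. The report should state that limitation.
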